## 7.2. TREATMENT SUMMARIZATION

In general, Stage 1 data will be presented by cohort/dose level as Cohort X (YY mg QD) [for example, Cohort 1 (100 mg QD)]. Stage 2 data will be summarized by cohort/disease group [for example, Cohort 1 (CLL)].

## 7.3. PRECISION

All PK concentrations will be reported and analyzed with the same precision as the source data provided by bioanalytical laboratory regardless of how many significant figures or decimals the data carry. Unrounded PK (exported from Phoenix WinNonlin) will be considered the source data for the calculation of descriptive statistics and the statistical analysis. Derived PK parameters will be rounded for reporting purposes in by-subject listings. For most derived PK parameters, 3 significant digits will be used as the standard rounding procedure, with the following exceptions:

- Parameters directly derived from source data (eg,  $C_{max}$  and  $C_{min}$ ) will be reported and analyzed with the same precision as the source data.
- Parameters derived from actual elapsed sample collection times (eg,  $t_{max}$  and  $t_{min}$ ) will be reported with the same precision as the actual elapsed sampling time value of the source data which shall be pre-specified as 2 decimal places with unit of hours.
- If a value is greater than 1000, it will be rounded to the nearest whole number.

For the reporting of descriptive statistics, the mean (arithmetic and geometric), and SD will be presented to one digit more precision than the source data. The minimum, median, and maximum will be presented to the same precision as the source data. Coefficient of variation and GCV will always be reported to 1 decimal place.

For inferential statistics, geometric least-squares (LS) mean ratios will be presented as a percentage (with 2 decimal places). P-values, if any, shall be reported to 4 decimal places or as  $<0.0001$ .

## 7.4. SOFTWARE VERSION

All derivations, statistical analyses, and associated statistical outputs (tables, figures, and

Document: 2018-523-00US1 PK SAP Final V1.0\_22Jun2023.docx

PPD

Version Number: Final 1.0

Version Date: 22Jun2023

CCI

---

 Statistical Analysis Plan for Pharmacokinetics
 

---

listings) will be generated using SAS Version 9.4 or higher (SAS Institute, Inc., Cary, North Carolina). Non-compartmental PK parameter calculations will be performed using Phoenix® WinNonlin® 8.3 or higher (Certara, Princeton, New Jersey). Graphics will be prepared using the same version of SAS.

## 8. STATISTICAL CONSIDERATIONS

### 8.1. MISSING DATA

Missing PK concentrations will be handled as described in [Section 10.1](#).

## 9. PROTOCOL DEVIATIONS

### 9.1. DEVIATIONS AND SIGNIFICANT EVENTS RELATED TO PK ANALYSIS

Changes to the procedures or events which may impact the quality of the PK data will be considered significant protocol deviations or events and will be described within the clinical study report body text. These changes or events will include any circumstances that will alter the evaluation of the PK. Examples include, but may not be limited to, dose or dosing regimen changes or missed doses that affect PK, concomitant medication usage likely to affect PK, vomiting following oral dosing occurring within the time frame of 2 times the median  $t_{max}$ , large time deviations at important time points, and sample processing errors that lead to inaccurate bioanalytical results. In the case of a significant protocol deviation or event, affected PK data may be excluded from analyses and summaries.

---

 Document: 2018-523-00US1 PK SAP Final V1.0\_22Jun2023.docx

 PPD
 [REDACTED]

Version Number: Final 1.0

Version Date: 22Jun2023

 CCI
 [REDACTED]
[REDACTED]
[REDACTED]

Statistical Analysis Plan for Pharmacokinetics

---

## 10. PHARMACOKINETICS

### 10.1. VARIABLES AND DERIVATIONS

#### 10.1.1. PLASMA CONCENTRATION DATA

A listing of PK blood sample collection times as well as derived sampling time deviations will be provided. A subject listing of all concentration-time data (HMPL-523 and its metabolites, including but not limited to M1 and M44) following HMPL-523 QD dosing will be presented by cohort/dose level/cycle, subject, and scheduled sample collection time.

Serial sampling concentration data will be summarized for the PKAS by stage, cohort/dose level, cycle, Day (1, 15, 28) and nominal time point using N, n, arithmetic mean, SD, CV, minimum, median, and maximum. Concentrations that are below the limit of quantitation (BLQ) will be treated as zero for the computation of descriptive statistics. If  $n < 3$ , then data will not be summarized, with the exception of n, minimum, and maximum. Unscheduled measurements will not be included in summary statistics. PK samples obtained in the Dose Expansion Stage within 14 to 28 days after a dose change will not be included in summary statistics. Listings will include all scheduled and unscheduled PK concentration data. In case a PK sample was collected outside the sampling windows defined in the protocol, the PK concentration results may be excluded from the summaries.

Graphs will be presented to illustrate the data for HMPL-523 (and metabolites if applicable) in Stage 1 and Stage 2 parts of the study as follows:

Stage 1 (Dose Escalation):

- Mean ( $\pm$ SD) concentration-time data by Day (Days 1, 15, and 28; one plot for each day with all dose levels in the same plot) for HMPL-523 (and metabolites if applicable) following QD administration will be presented on linear and semilogarithmic scale.
- Mean ( $\pm$ SD) concentration-time data for HMPL-523 (and metabolites if applicable) by dose level (one plot for each dose level with all days in the same plot) following QD administration will be presented on linear and semilogarithmic scale.
- By-subject plots with concentration profiles for HMPL-523 (and metabolites if applicable)

Document: 2018-523-00US1 PK SAP Final V1.0\_22Jun2023.docx

PPD

Version Number: Final 1.0

Version Date: 22Jun2023

CCI

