5.4 Dose Delays and Modification

5.4.1 During Dose-Limiting Toxicity Assessment Window

If a patient experiences a TEAE of Grade 3 or Grade 4 and/or unacceptable toxicity including a DLT not attributable to the disease or disease-related processes under investigation, dosing will be interrupted and supportive therapy will be administered as required in accordance with local practices/guidelines.

Patients who experience a DLT may resume dosing at the same or the previous lower dose level at the discretion of the investigator if the toxicity is resolved or improved to baseline level. If a patient experiences an unacceptable toxicity at the reduced dose level, he/she will be discontinued from treatment. No patient will have his/her dose reduced by more than 2 dose levels. Once dose is reduced, it cannot be re-escalated.

If a clinically significant TEAE or unacceptable toxicity that does not meet the definition of a DLT is observed, the patient may receive subsequent doses to complete the dosing schedule, provided that the TEAE is improved to CTCAE Grade ≤ 2 within 2 weeks.

Dose reduction in patients without DLT is not permitted in the DLT assessment window without the sponsor's approval.

5.4.2 After Dose-Limiting Toxicity Assessment Window in Stage 1 or in Stage 2

After the DLT assessment window in Stage 1 or in Stage 2, the dose of HMPL-523 may be interrupted and/or reduced to the next lower dose level (600 mg) if any of the following are observed:

- Grade 3 or 4 hematologic toxicity
- Grade 3 or 4 nonhematologic toxicity (except for alopecia and skin eruption, nausea, vomiting, diarrhea, or constipation if well-controlled by systemic or topical medication)

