### 7.1. SUMMARY STATISTICS

Plasma concentrations of HMPL-523 and its metabolites will be summarized separately for Stage 1 and Stage 2 as appropriate (for  $n \geq 3$  only) by cohort/dose level, cycle, day, and nominal time point using  $N$  (number of subjects),  $n$  (number of observations), arithmetic mean, standard deviation (SD), coefficient of variation (CV), minimum, median, and maximum using the PK analysis set. If  $n < 3$ , then only  $n$ , minimum, and maximum will be presented. Stage 2 serial sampling concentration data collected after a dose change will only be included in listings.

Pharmacokinetic parameters for HMPL-523 and its metabolites will be summarized separately for Stage 1 and Stage 2 as appropriate (for  $n \geq 3$  only) by cohort/dose level, cycle, and day using  $N$ ,  $n$ , arithmetic mean, SD, CV, minimum, median, maximum, geometric mean (GeoMean), and geometric CV (GCV) using the PK analysis set. If  $n < 3$ , then only  $n$ , minimum, and maximum will be presented. Arithmetic mean, SD, CV, GeoMean, and GCV will not be calculated for  $t_{\max}$  and  $t_{\min}$ . A subject listing of individual PK parameters for each treatment will be provided. Stage 2 PK parameters calculated from serial sampling concentration data collected after a dose change will only be included in listings.

Document: 2018-523-00US1 PK SAP Final V1.0\_22Jun2023.docx

PPD

Version Number: Final 1.0

Version Date: 22Jun2023

CCI

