## Statistical Analysis Plan for Pharmacokinetics

---

on Days 1, 15, and 28 will be presented on linear and semilogarithmic scale in the same graph.

- Mean ( $\pm$ SD) trough concentrations on Cycle 1 Day 2, Day 15 ( $\pm$ 1), Day 16 ( $\pm$ 1), and Day 28 ( $\pm$ 3) and Cycle 2 Day 1 ( $\pm$ 3) (ie, Day 29 relative to Cycle 1) will be presented for HMPL-523 (and metabolites if applicable) on a linear scale as scatter plots versus time in days from start of treatment (numeric scale) for each cohort/dose level. Attainment of steady state for HMPL-523 will be evaluated graphically by evaluating these trough concentrations over this period.

Stage 2 (Dose Expansion Stage):

- Mean ( $\pm$ SD) concentration-time data for HMPL-523 (and metabolites if applicable) at RP2D by Day (all disease groups with  $n \geq 3$  in one plot) following QD administration will be presented on linear and semilogarithmic scale.
- By-subject plots with concentration profiles for HMPL-523 (and metabolites if applicable) by Day will be presented on linear and semilogarithmic scale in the same graph.
- Mean ( $\pm$  SD) trough concentrations on Cycle 1 Day 2 and Day 28 ( $\pm$ 3), Cycle 2 Day 1 ( $\pm$ 3), Cycle 3 Day 1 ( $\pm$ 3), Cycle 5 Day 1 ( $\pm$ 3) and every other cycle thereafter will be presented for HMPL-523 (and metabolites if applicable) at RP2D on a linear scale as scatter plots versus time in days from start of treatment (numeric scale) for each disease group.

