 Statistical Analysis Plan for Pharmacokinetics
 

---

$AUC_{\tau}/D$	Dose-Normalized $AUC_{\tau}$ , calculated as $AUC_{\tau}$ divided by dose.
----------------	--

The following plasma PK parameters will be estimated for HMPL-523 (and metabolites if applicable) following multiple dosing on Days 15 and 28 of Cycle 1 for Stage 1 and Day 28 of Cycle 1 (and 14-28 days after a dose change in subsequent cycles) for Stage 2 where data is collected and available:

$C_{\max}$	Maximum concentration after multiple dosing, obtained directly from the observed concentration versus time data.
$t_{\max}$	Time of maximum concentration, obtained directly from the observed concentration versus time data.
$C_{\min}$	Minimum observed concentration after multiple dosing, obtained directly from the observed concentration versus time data.
$t_{\min}$	Time of minimum concentration, obtained directly from the observed concentration versus time data.
$AUC_{\tau}$	
Area under the plasma concentration-time curve during a dosing interval (<math>\tau = 24</math> h), calculated by linear up/log down trapezoidal summation. Actual elapsed time will be used for the calculation, unless otherwise specified below.
 
The following conventions will be followed for missing or BLQ data at <math>\tau</math> on study Days 15 and 28 (Cycle 1):
 
 
• If the concentration at predose is missing, then the concentration will be set to equal the concentration measured at <math>\tau</math> [assuming linear PK and steady-state conditions, and that the <math>\tau</math> sample was collected within a window of <math>\pm 1</math> hour of the scheduled time postdose for the calculation of <math>AUC_{\tau}</math> but prior to the next dose].
 
• If no sample is collected at the end of the dosing interval or data are missing at the end of the dosing interval, the concentration will be set equal to the predose value (assuming linear PK and steady-state conditions, and that the predose collection was valid) and <math>\tau</math> will be set to the nominal time for the calculation of <math>AUC_{\tau}</math>, if appropriate.
 
• <math>AUC_{\text{all}}</math> (if appropriate) shall be used as an estimate of <math>AUC_{\tau}</math> if
 

Document: 2018-523-00US1 PK SAP Final V1.0\_22Jun2023.docx

 PPD
 [REDACTED]

Version Number: Final 1.0

Version Date: 22Jun2023

 CCI
 [REDACTED]
[REDACTED]
[REDACTED]

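### The PK SAP has no mandatory dose-at-sampling rule for Stage 2 single troughs or Stage 1 Day 15/28 data, and its accumulation ratio ignores dose changes

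*SAP*

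**What the plan says.** Several rules in the PK SAP bear on samples taken after a dose change.

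- Section 10.1.1, Stage 2, with a time band: "PK samples obtained in the Dose Expansion Stage within 14 to 28 days after a dose change will not be included in summary statistics". The band matches the timing of the extra profile described in section 10.1.2, where multiple-dose parameters are estimated on Day 28 of Cycle 1 "and 14-28 days after a dose change in subsequent cycles) for Stage 2 where data is collected and available".
- Section 7.1, Stage 2, with no time band but serial data only: "Stage 2 serial sampling concentration data collected after a dose change will only be included in listings". For parameters: "Stage 2 PK parameters calculated from serial sampling concentration data collected after a dose change will only be included in listings". Section 10.1.2 repeats the parameter rule.
- Section 9.1, both stages: "dose or dosing regimen changes or missed doses that affect PK" is listed as an example of a significant event, and then "affected PK data may be excluded from analyses and summaries".
- Section 10.1.1, Stage 2 trough plot: troughs on Cycle 1 Days 2 and 28, Cycle 2 Day 1, Cycle 3 Day 1, Cycle 5 Day 1 "and every other cycle thereafter will be presented for HMPL-523 (and metabolites if applicable) at RP2D".

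Section 7.1 also has a general instruction to summarise concentrations by cohort or dose level, cycle, day and nominal time. Section 7.2 groups Stage 2 by disease cohort and mentions no split by dose actually taken.

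Protocol section 5.4.2 names 600 mg and 400 mg as the reduced doses below the 700 mg RP2D. For the first cycle, Protocol section 5.4.1 says: "Patients who experience a DLT may resume dosing at the same or the previous lower dose level at the discretion of the investigator". Section 10.1.2 of the PK SAP defines the accumulation ratio as AUCtau (or Cmax) on Day 15 or 28 divided by the same quantity on Day 1, without reference to dose.

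**The concern.** The 14-28 day band says when the extra post-change profile is taken. It does not say when a trough stops reflecting the assigned dose: a patient reduced to 400 mg is still on 400 mg at day 29 and at day 90. Applied literally, the band removes a reduced-dose trough at one visit and leaves the same patient's trough, on the same dose, at the next.

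The rule without a time limit does not help, because it covers serial sampling only. Cycle 3 Day 1, Cycle 5 Day 1 and later samples are single pre-dose draws.

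At stake is whether the Stage 2 cohort summaries describe 700 mg. If reduced-dose troughs are included, and reductions accumulate over time, mean troughs will drift down across cycles for a reason unrelated to how the drug behaves at 700 mg. In Stage 1, a mid-cycle reduction would lower the accumulation ratio and the later-day troughs in the section 10.1.3 steady-state model, which takes all valid concentrations without defining valid. Characterising PK in both stages is a secondary objective (Protocol section 3.2).

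**Working it through.** The plan gives no figure to reproduce. The check is which samples each rule reaches, and how large the effect could be.

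**1. Reach of the 14-28 day band.** Inputs: 28-day cycles with no delay (an assumption) and the sampling days in Protocol Appendix 3. Cycle 3 Day 1 is study day 2 × 28 + 1 = 57. Cycle 5 Day 1 is 4 × 28 + 1 = 113. A trough on day T is caught if the dose changed on day d with 14 ≤ T − d ≤ 28.

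- T = 57: d from 29 to 43, which is 15 of the 55 possible change days 2-56 (27%).
- T = 113: d from 85 to 99, which is 15 of the 111 possible change days 2-112 (14%).

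These are shares of calendar days, not of patients.

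Two examples:
- Change on Day 40: Cycle 3 Day 1 is 17 days later and is dropped. Cycle 5 Day 1 is 73 days later and is not caught.
- Change on Day 50: Cycle 3 Day 1 is 7 days later and is not caught.

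Cycle 1 Day 28 and its 24-hour sample at Cycle 2 Day 1 form a serial profile, so section 7.1 already removes them after any dose change.

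**2. Possible size for troughs.** Protocol section 2.2.4.5 reports roughly dose-proportional steady-state Cmax and AUCtau over 100-700 mg. Extending that to troughs is an assumption. The ratios to 700 mg are 600/700 = 0.857 and 400/700 = 0.571. If a share p of the troughs is at the lower dose, the arithmetic mean shifts by p × (ratio − 1).

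| p | all at 600 mg | all at 400 mg |
|---|---|---|
| 0.10 | −1.4% | −4.3% |
| 0.20 | −2.9% | −8.6% |
| 0.30 | −4.3% | −12.9% |

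The documents do not report how many patients had reductions, so p is assumed. In a small cohort one patient matters more: one of three at 400 mg gives 1/3 × (0.571 − 1) = −14.3%.

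**3. Accumulation ratio.** Protocol section 2.2.4.5 gives a mean ratio of about 1.60. Under dose proportionality, the raw ratio after a reduction is 1.60 × (later dose / Day 1 dose). For 600 to 400 mg: 1.60 × 400/600 = 1.07. For 800 to 600 mg: 1.60 × 600/800 = 1.20. The error carries into the effective half-life, defined in section 10.1.2 as −0.693 × 24 / ln(1 − 1/ratio). A ratio of 1.60 gives 16.63/0.981 = 17.0 h, and 1.067 gives 16.63/2.773 = 6.0 h.

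**The case against.** The other side has several good points.

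- **Stage 2 serial data are already protected.** A reader might infer that the 14-28 day sentence is the only Stage 2 exclusion. It is not: section 7.1 sends all serial concentrations and their parameters after a dose change to listings, so no Stage 2 Cmax or AUCtau obtained on a reduced dose enters a summary.
- **Nothing directs that reduced-dose troughs be kept.** The concentration table in section 10.1.1 covers serial data on Days 1, 15 and 28. The only output that names the later troughs is the plot, which is labelled for the RP2D. That stands for the plot. But the general instruction in section 7.1 also reaches those troughs, and since every Stage 2 patient is assigned the RP2D, the label can be read as a cohort name. The text is ambiguous.
- **Stage 1 is not without a rule.** Section 9.1 applies to both stages and names dose changes. It is discretionary, however. The PKAS definition in section 6.2 does not fill the gap, because one clean concentration admits a patient to all PK analyses.
- **Reach is limited.** Amendment 5 stops PK samples from Cycle 5 Day 1 onward. A Cycle 1 reduction in Stage 1 needs a DLT or the sponsor's approval. The 800 mg steady-state data were too sparse for the protocol's own summary. Dose-normalised Cmax and AUCtau are already planned. Still, about 3 of 48 expansion patients remained on treatment at Amendment 5, so most late troughs would already have been taken.
- **The shift is small against the noise.** Between-subject variability was around 60-80% in the Australian study (Protocol section 2.2.4.3), so the relative standard error of a mean is 12-16% with n = 25 (60/√25 to 80/√25) and 23-30% with n = 7. By Protocol Table 2 only the HL (25), PTCL (9) and CLL post-BTK (7) cohorts could reach the minimum of three for summary means. This is fair as to scale, but a one-directional bias is not excused by a wide interval.

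A reader might also expect a false decline to be taken for auto-induction. The protocol calls the drug only a possible weak CYP3A inducer, and no Stage 2 test of troughs over time is planned, so that step is speculative.

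**Conclusion.** The point holds as a gap and an inconsistency between rules, not as an instruction to pool doses. Stage 2 single troughs on a reduced dose are not required to leave the cohort summaries unless they fall 14-28 days after the change, a band with no bearing on whether the trough represents 700 mg. Stage 1 Day 15/28 data after a reduction have only a discretionary rule, exercised when concentrations may already be known. The raw accumulation ratio is wrong whenever the two doses differ.

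The size of the effect is unknown. About 3-13% low for mean late troughs rests on two assumptions: 20-30% of them at 600 or 400 mg, and dose-proportional troughs. The outputs are descriptive and secondary, and no primary conclusion depends on them. The change is worth making because it is cheap and because the present rule, followed literally, treats identical doses differently.

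**What to change.** Reconcile PK SAP sections 7.1, 9.1, 10.1.1 (text and plot) and 10.1.2 into one mandatory rule for both stages, for example: *Any concentration or parameter obtained while the patient was taking a dose other than the assigned dose will be listed, and excluded from summaries, plots and the steady-state model for the assigned dose, whatever the time since the change.* State which dose enters the dose-proportionality model for such patients.

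For the accumulation ratio, use AUCtau/D and Cmax/D when the Day 1 and Day 15/28 doses differ, or do not report it. Treat the effective half-life in the same way.

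The cost is a few sentences and one filter on dose at sampling. For Stage 2, Protocol Appendix 3 already requires dosing dates and times on the PK day and the day before to be recorded.

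The downside is fewer late troughs, and possible selection. If reductions fall mainly on high-exposure patients (plausible, but not stated in the documents), dropping them leaves lower-exposure patients and could itself produce a decline over cycles. So also present dose-normalised troughs with the reduced-dose patients included, and give the number at each dose by visit.

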## Statistical Analysis Plan for Pharmacokinetics

---

on Days 1, 15, and 28 will be presented on linear and semilogarithmic scale in the same graph.

- Mean ( $\pm$ SD) trough concentrations on Cycle 1 Day 2, Day 15 ( $\pm$ 1), Day 16 ( $\pm$ 1), and Day 28 ( $\pm$ 3) and Cycle 2 Day 1 ( $\pm$ 3) (ie, Day 29 relative to Cycle 1) will be presented for HMPL-523 (and metabolites if applicable) on a linear scale as scatter plots versus time in days from start of treatment (numeric scale) for each cohort/dose level. Attainment of steady state for HMPL-523 will be evaluated graphically by evaluating these trough concentrations over this period.

Stage 2 (Dose Expansion Stage):

- Mean ( $\pm$ SD) concentration-time data for HMPL-523 (and metabolites if applicable) at RP2D by Day (all disease groups with  $n \geq 3$  in one plot) following QD administration will be presented on linear and semilogarithmic scale.
- By-subject plots with concentration profiles for HMPL-523 (and metabolites if applicable) by Day will be presented on linear and semilogarithmic scale in the same graph.
- Mean ( $\pm$  SD) trough concentrations on Cycle 1 Day 2 and Day 28 ( $\pm$ 3), Cycle 2 Day 1 ( $\pm$ 3), Cycle 3 Day 1 ( $\pm$ 3), Cycle 5 Day 1 ( $\pm$ 3) and every other cycle thereafter will be presented for HMPL-523 (and metabolites if applicable) at RP2D on a linear scale as scatter plots versus time in days from start of treatment (numeric scale) for each disease group.

